**8.9.6. Listings****Listing 16.2.6.9: Total FACIT fatigue score**

Listing per treatment group, per subject and per time point of the total score: actual values, changes from baseline and percent changes from baseline. The original 13 items will not be listed.

Population: ITT.

## 8.10. QUALITY OF LIFE: SF-36

### 8.10.1. Parameters

The SF-36 (version 2) consists of 36 items.

The 36 questions:

- *1: In general, would you say your health is*
- *2: Compared to one year ago, how would you rate your health in general now*
- *3A: Vigorous activities, such as running, lifting heavy objects, participating in strenuous sports*
- *3B: Moderate activities, such as moving a table, pushing a vacuum cleaner, bowling, or playing golf*
- *3C: Lifting or carrying groceries*
- *3D: Climbing several flights of stairs*
- *3E: Climbing one flight of stairs*
- *3F: Bending, kneeling, or stooping*
- *3G: Walking more than a mile*
- *3H: Walking several hundred yards*
- *3I: Walking one hundred yards*
- *3J: Bathing or dressing yourself*
- *4A: As a result of your physical health, cut down on the amount of time you spent on work or other activities*
- *4B: As a result of your physical health, accomplished less than you would like*
- *4C: As a result of your physical health, were limited in the kind of work or other activities*
- *4D: As a result of your physical health, had difficulty performing the work or other activities (for example, it took extra effort)*
- *5A: As a result of any emotional problems, cut down the amount of time you spent on work or other activities*
- *5B: As a result of any emotional problems, accomplished less than you would like*
- *5C: As a result of any emotional problems, did work or other activities less carefully than usual*
- *6: During the past 4 weeks, to what extent has your physical health or emotional problems interfered with your normal social activities with family, friends, neighbors, or groups*
- *7: How much bodily pain have you had during the past 4 weeks*
- *8: During the past 4 weeks how much did pain interfere with your normal work (including both work outside the home and housework)*
- *9A: How much of the time during the past 4 weeks: did you feel full of life*

- 9B:How much of the time during the past 4 weeks: have you been very nervous
- 9C:How much of the time during the past 4 weeks: have you felt so down in the dumps that nothing could cheer you up
- 9D:How much of the time during the past 4 weeks: have you felt calm and peaceful
- 9E:How much of the time during the past 4 weeks: did you have a lot of energy
- 9F:How much of the time during the past 4 weeks: have you felt downhearted and depressed
- 9G:How much of the time during the past 4 weeks: did you feel worn out
- 9H:How much of the time during the past 4 weeks: have you been happy
- 9I:How much of the time during the past 4 weeks: did you feel tired
- 10:During the past 4 weeks, how much of the time has your physical health or emotional problems interfered with your social activities (like visiting your friends, relatives, etc.)
- 11A:I seem to get sick a little easier than other people
- 11B:I am as healthy as anybody I know
- 11C:I expect my health to get worse
- 11D:My health is excellent

**General comments:** The coding and scoring for each component (PCS, MCS) is done according to the tables below.

#### Coding and Scoring for the 8 SF-36 (Version 2) Scales

Scale	Item	Coding (makes use of QSRCCD)	Range of raw score	Normalization*
Physical functioning	Items 3a to 3j	Yes, limited a lot=1 Yes, limited a little=2 No, not limited=3	10-30	(S-10)/20x100
Role-physical	Items 4a to 4d	All of the time = 1 Most of the time = 2 Some of the time = 3 A little of the time = 4 None of the time = 5	4-20	(S-4)/16x100
Bodily pain	Item 7	None=6 Very mild=5.4 Mild=4.2 Moderate=3.1 Severe=2.2 Very severe=1	2-12	(S-2)/10x100
	Item 8 if both items 7 and 8 are answered	Not at all and item7 eq 'None' = 6 Not at all and item7 not equal 'None' = 5		

Scale	Item	Coding (makes use of QSRCCD)	Range of raw score	Normalization*
		A little bit = 4 Moderately = 3 Quite a bit = 2 Extremely = 1		
	Item 8 if item 7 is not answered	Not at all =6 A little bit = 4.75 Moderately =3.5 Quite a bit = 2.25 Extremely = 1		
General health	Item 1	Excellent = 5 Very good = 4.4 Good = 3.4 Fair = 2 Poor = 1	5-25	(S-5)/20x100
	Items 11a and 11c	Definitely true = 1 Mostly true = 2 Don't know = 3 Mostly false = 4 Definitely false = 5		
	Items 11b and 11d	Definitely true = 5 Mostly true = 4 Don't know = 3 Mostly false = 2 Definitely false = 1		
Vitality	Items 9a and 9e	All of the time = 5 Most of the time = 4 Some of the time = 3 A little of the time = 2 None of the time = 1	4-20	(S-4)/16x100
	Items 9g and 9i	All of the time = 1 Most of the time = 2 Some of the time = 3 A little of the time = 4 None of the time = 5		
Social functioning	Item 6	Not at all = 5 Slightly = 4 Moderately = 3 Quite a bit = 2	2-10	(S-2)/8x100

Scale	Item	Coding (makes use of QSRCCD)	Range of raw score	Normalization*
		Extremely = 1		
	Item 10	All of the time = 1 Most of the time = 2 Some of the time = 3 A little of the time = 4 None of the time = 5		
Role-emotional	Items 5a to 5c	All of the time = 1 Most of the time = 2 Some of the time = 3 A little of the time = 4 None of the time = 5	3-15	(S-3)/12x100
Mental health	Items 9b, 9c and 9f	All of the time = 1 Most of the time = 2 Some of the time = 3 A little of the time = 4 None of the time = 5	5-25	(S-5)/20x100
	Items 9d and 9h	All of the time = 5 Most of the time = 4 Some of the time = 3 A little of the time = 2 None of the time = 1		
*S = raw score = sum of item scores after coding				

For the 8 raw scale scores calculations, if at least 50% of the items comprising a scale have non-missing responses, impute the average score calculated for the non-missing scale items for the missing items of the same scale. If more than 50% of scale items comprising a scale are missing a response, set the scale to missing.

Then each scale score needs to be standardized (z-score) as below:

**Standardization of the SF-36 (Version 2) Scale Scores**

Item	Standardization (Z-score)
Physical functioning	$PF\_Z = (PF-83.29094)/23.75883$
Role-physical	$RP\_Z = (RP-82.50964)/25.52028$
Bodily pain	$BP\_Z = (BP-71.32527)/23.66224$
General health	$GH\_Z = (GH-70.84570)/20.97821$
Vitality	$VT\_Z = (VT-58.31411)/20.01923$
Social functioning	$SF\_Z = (SF-84.30250)/22.91921$
Role-emotional	$RE\_Z = (RE-87.39733)/21.43778$
Mental health	$MH\_Z = (MH-74.98685)/17.75604$

Note: Based on the 1998 general United States population.

Finally, the SF-36 physical and mental component transformed scores are calculated using the below conventions.

**SF-36 Aggregate Component and Transformed Scores**

Score	Calculation
Aggregate Standardized Score	
Physical component	$AGG\_PHYS = (PF\_Z * 0.42402) + (RP\_Z * 0.35119) +$ $(BP\_Z * 0.31754) + (GH\_Z * 0.24954) + (VT\_Z * 0.02877) +$ $(SF\_Z * -0.00753) + (RE\_Z * -0.19206) + (MH\_Z * -0.22069)$
Mental component	$AGG\_MENT = (PF\_Z * -0.22999) + (RP\_Z * -0.12329) +$ $(BP\_Z * -0.09731) + (GH\_Z * -0.01571) + (VT\_Z * 0.23534) +$ $(SF\_Z * 0.26876) + (RE\_Z * 0.43407) + (MH\_Z * 0.48581)$
Transformed Summary	
Transformed physical	$PCS = 50 + (AGG\_PHYS * 10)$
Transformed mental	$MCS = 50 + (AGG\_MENT * 10)$

In addition, the 8 scale scores will be reported in norm-based transformation. Norm-based transformation will be achieved by multiplying each z-score by 10 and adding 50 to it:

Item	Norm-based transformation of the z-scores
Physical functioning	Norm-based PF = 50 + (PF_Z*10)
Role-physical	Norm-based RP = 50 + (RP_Z*10)
Bodily pain	Norm-based BP = 50 + (BP_Z*10)
General health	Norm-based GH = 50 + (GH_Z*10)
Vitality	Norm-based VT = 50 + (VT_Z*10)
Social functioning	Norm-based SF = 50 + (SF_Z*10)
Role-emotional	Norm-based RE = 50 + (RE_Z*10)
Mental health	Norm-based MH = 50 + (MH_Z*10)

Derivation of these summary scores, including appropriate handling of missing items, will be done using the scoring software provided by the owner of the scale (QualityMetrics).

Please refer to the SF-36 v2 manual for additional information.

The analysis will present the 2 summary component measures and the 8 domains:

- Transformed physical component scale PCS and mental component scale MCS
- Norm-based physical functioning (PF), role physical (RF), bodily pain (BP), general health (GH), vitality (VT), social functioning (SF), role emotional (RE) and mental health (MH)

The analysis will present actual values, changes from baseline and percent changes from baseline in the above-mentioned scores.

Note that the percentage change from baseline remains missing if the baseline value itself equals zero.

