#### **8.7.1.1.6 36-Item Short-form Health Survey (SF-36)**

The health-related quality of life of the subject will be assessed using the SF-36 (version 2) with a 4-week recall period. This consists of 36 questions belonging to 8 domains in 2 components:

- Physical well-being: 4 domains: physical functioning (10 items), role physical (4 items), bodily pain (2 items), and general health perceptions (5 items).
- Mental well-being: 4 domains: vitality (4 items), social functioning (2 items), role emotional (3 items), and mental health (5 items).

The remaining item (health transition) is not part of the above domains but is kept separately (Appendix 13.7).

These scales will be rescaled from 0 to 100 (converting the lowest possible score to 0 and the highest possible score to 100), with higher scores indicating a better quality of life.

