#### **Table 14.2.1.10.1:SF-36: Descriptive statistics of the actual values**

#### **Table 14.2.1.10.2:SF-36: Descriptive statistics of the change from baseline**

#### **Table 14.2.1.10.3:SF-36: Descriptive statistics of the percent change from baseline**

(descriptive statistics at each time point; frequency table at weeks 12 + 24)

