#### **Table 14.2.1.10.4:SF-36: Summary with overall p-value and pairwise comparisons versus placebo**

**Table 14.2.1.10.5: SF-36: Exploratory pairwise comparisons among the dose groups within each regimen****Table 14.2.1.10.6: SF-36: Exploratory pairwise comparisons between regimens within each daily dose level****8.10.3. Figures over the whole 24 weeks period**

Line plots showing baseline, Week 4, 12 and 24. Same analysis as for the DAS28(CRP). Population: ITT. LOCF only. Both main scores as well as the 8 subdomains will be presented.

**Figure 14.2.1.10.1: SF-36: Plot of the actual values over time****Figure 14.2.1.10.2: SF-36: Plot of the changes from baseline over time****Figure 14.2.1.10.3: SF-36: Plot of the percent changes from baseline over time****8.10.4. Tables after Week 12**

Tables will present Weeks 4, 12 and 24, unless specified otherwise, for the 15 arms of “efficacy chapter 3”. The same descriptive analysis as DAS28(CRP) will be performed. Analysis population: ITT. LOCF and observed case (weeks 12 + 24). Tables will present the 8 domain scores and the 2 main scores.

**Table 14.2.1.10.7: SF-36 after Week 12: Descriptive statistics of the actual values****Table 14.2.1.10.8: SF-36 after Week 12: Descriptive statistics of the change from baseline****Table 14.2.1.10.9: SF-36 after Week 12: Descriptive statistics of the percent change from baseline****8.10.5. Figures after Week 12**

No figures planned.

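### SF-36 percent changes are planned on norm-based scores whose zero is set by scoring constants, so their size depends on those constants as well as on improvement and cannot be compared across domains

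*SAP*

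**What the plan says.** SAP 8.10.1 builds the SF-36 scores in three steps. Each domain is first brought to a 0-100 scale (the Normalization column of the coding table). It is then standardized with a mean and SD from the 1998 US general population. Finally it is made norm-based: "Norm-based transformation will be achieved by multiplying each z-score by 10 and adding 50 to it". The two component scores, PCS and MCS, are likewise 50 plus 10 times a weighted sum of the standardized domains. The scores to be presented are PCS, MCS and the eight norm-based domains, and the section then says: "The analysis will present actual values, changes from baseline and percent changes from baseline in the above-mentioned scores". The percentage is left missing only when the baseline equals zero.

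The outputs are "Table 14.2.1.10.3:SF-36: Descriptive statistics of the percent change from baseline" (with a frequency table at Weeks 12 and 24), "Figure 14.2.1.10.3: SF-36: Plot of the percent changes from baseline over time", and the post-Week 12 counterpart, Table 14.2.1.10.9.

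Protocol 8.7.1.1.6 describes the domain scales differently: "These scales will be rescaled from 0 to 100 (converting the lowest possible score to 0 and the highest possible score to 100". On that scale a larger value is the better one. Protocol 8.8.1.3 leaves the (sub)totals to the instrument's scoring algorithm.

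Formal comparisons are a separate matter. SAP 6.1.2.3 restricts them to absolute changes from baseline and plans SF-36 comparisons by AN(C)OVA on those changes.

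**The concern.** A percent change has a ratio meaning only if the scale has a zero that stands for none of the quantity. On a score of 50 + 10z, zero is the point five reference SDs below the reference mean. It does not mean worst health, and no domain score can reach it. Dividing by the baseline therefore divides by a distance to an arbitrary point, and that point differs from domain to domain.

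Quality of life is a secondary objective. Two tables and a figure would print percentages for ten scores together, which invites the reader to judge where the drug helps most by comparing them. Part of any such ranking would come from the reference means and SDs.

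A second problem lies in the frequency table. SAP 8.10.2 refers SF-36 to the DAS28(CRP) analysis, and SAP 8.4.2 refers DAS28(CRP) to the SDAI/CDAI analysis. The percent-change classes given there (Table 14.2.1.3.3) are one class for zero or above and ten bands running down to -100. They suit scores where a fall is good. On SF-36 a rise is good.

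**Working it through.** The documents give no SF-36 percent figure to reproduce and no SF-36 baseline values, so the raw scores below are illustrative assumptions. The constants are the SAP's own.

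**Inputs (SAP 8.10.1, standardization table), mean and SD:** PF 83.29094, 23.75883; RP 82.50964, 25.52028; BP 71.32527, 23.66224; GH 70.84570, 20.97821; VT 58.31411, 20.01923; SF 84.30250, 22.91921; RE 87.39733, 21.43778; MH 74.98685, 17.75604.

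**Formula.** For a 0-100 score x, T(x) = 50 + 10(x - mean)/SD. T is zero at x = mean - 5 SD. The percent change from x0 to x1 therefore reduces to 100(x1 - x0) / [x0 - (mean - 5 SD)].

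**Where the zero lies.** For bodily pain, 71.32527 - 5(23.66224) = -46.99. For mental health, 74.98685 - 5(17.75604) = -13.79. Both lie below the bottom of the 0-100 scale, and the same holds for every domain.

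**Same change in every domain, 30 to 45 (+50% on 0-100):**
- Bodily pain: 15 / (30 + 46.99) = +19.5%.
- Mental health: 15 / (30 + 13.79) = +34.3%.

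| Domain | T at 0 | T at 30 | T at 45 | Points | Percent |
|---|---|---|---|---|---|
| PF | 14.94 | 27.57 | 33.88 | 6.31 | +22.9 |
| RP | 17.67 | 29.42 | 35.30 | 5.88 | +20.0 |
| BP | 19.86 | 32.54 | 38.87 | 6.34 | +19.5 |
| GH | 16.23 | 30.53 | 37.68 | 7.15 | +23.4 |
| VT | 20.87 | 35.86 | 43.35 | 7.49 | +20.9 |
| SF | 13.22 | 26.31 | 32.85 | 6.54 | +24.9 |
| RE | 9.23 | 23.23 | 30.22 | 7.00 | +30.1 |
| MH | 7.77 | 24.66 | 33.11 | 8.45 | +34.3 |

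The ratio of largest to smallest percentage is 34.3/19.5 = 1.76. For points it is 8.45/5.88 = 1.44.

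**Dependence on the constant.** Take a patient moving from z = -1.8 to z = -1.0. The change is +8 points whatever the origin. With origin 50 the percentage is 8/32 = +25.0%. With origin 100 it would be 8/82 = +9.8%.

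**Dependence on improvement, origin fixed at 50.** From a baseline of 32, gains of 0, 2, 5, 8 and 10 points give 0, 6.2, 15.6, 25.0 and 31.2%. A gain of 8 points is 40% from a baseline of 20 and 16% from a baseline of 50.

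**The zero-baseline rule.** The lowest attainable domain scores run from 7.8 (MH) to 20.9 (VT), so the rule can never apply to a domain. If each domain is set to 0 or 100 by the sign of its weight, the algebraic lower bound is 0.65 for PCS and -8.81 for MCS. The rule does not cover a component score that is near zero or negative.

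**Frequency classes.** With a positive baseline, any SF-36 improvement gives a positive percentage. In the SDAI/CDAI classes it falls into the zero-or-above class together with patients who did not change. The ten remaining bands would describe only worsening.

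**The case against.** Several stronger readings are tempting, and the documents do not support them.

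- *The percentage says nothing about improvement.* It does. At a given positive baseline it keeps the sign of the point change, is zero when nothing changes and is proportional to it. All arms share the same constants, so within a domain no arm is favoured by construction.
- *The SF-36 results or p-values are affected.* They are not. SAP 6.1.2.3 puts the formal comparisons on absolute changes, and point changes are already planned in Tables 14.2.1.10.2 and 14.2.1.10.8 and Figure 14.2.1.10.2.
- *Benefit is shown as too small.* That holds only relative to the 0-100 scale, whose own zero is the lowest item-coding sum and thus also a convention.
- *The protocol promised 0-100 tables.* It describes the rescaling, which the SAP performs, and leaves (sub)totals to the scoring algorithm.
- *Negative or near-zero component scores will distort the tables.* The MCS bound of -8.81 needs perfect physical function, role-physical, pain and general health together with the worst vitality, social, role-emotional and mental health scores. That is implausible in patients with at least 6 swollen and 8 tender joints.

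Two further objections stand in part. Some of the cross-domain spread is deliberate standardization and survives in norm-based points (1.44-fold against 1.76-fold in the example). The protocol is also not clear that SF-36 percent change was never intended: section 8.8.1.3 lists percent changes for continuous parameters generally, while its quality-of-life paragraph names only changes from Baseline.

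The separate mock tables may define suitable SF-36 classes. The SAP text gives none.

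**Conclusion.** The point holds as a defect of descriptive presentation. The planned SF-36 percent changes have no ratio meaning. Their size reflects the constant 50 and the US reference norms as well as the patient's improvement, and they cannot be compared across domains. In the worked example one and the same 0-100 change prints anywhere from +19.5% to +34.3%. The zero-baseline rule offers no protection for domain scores. If the SDAI/CDAI classes are inherited, the frequency table cannot show degrees of improvement.

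The reach is Tables 14.2.1.10.3 and 14.2.1.10.9 and Figure 14.2.1.10.3. No planned p-value or confidence interval depends on them. The numerical examples rest on the SAP's constants and on assumed raw scores, so they show the mechanism and not the distortion to be expected in this trial. The point about the classes rests on the SAP text alone.

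**What to change.** Delete percent change for PCS, MCS and the norm-based domains in SAP 8.10.1, and with it Tables 14.2.1.10.3 and 14.2.1.10.9 and Figure 14.2.1.10.3. Remove the matching entries from Listing 16.2.6.10. Rely on Tables 14.2.1.10.2 and 14.2.1.10.8 and Figure 14.2.1.10.2 for change in points.

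Attach the Week 12 and Week 24 frequency table to the point-change output. State its classes in the SAP as ranges of point change, with higher being better. The SAP already does this for HAQ-DI in Table 14.2.1.7.2, with the direction suited to that scale.

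Do not move the percentage to the 0-100 domain scores as a fallback. A patient at the bottom of a domain has a baseline of 0 there, the percentage is then missing under the SAP's rule, and the worst patients drop out of the summary.

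The cost is a change of SAP wording and mocks, and the loss of descriptive percent-change outputs that no inference uses. Because the protocol's general wording on continuous parameters could be read to include SF-36, record the deletion in SAP 6.3. The remaining point changes will still differ somewhat between domains for the same 0-100 change, as norm-based scoring intends.

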### **8.10.2. Tables over the whole 24 weeks period**

Same analysis as for the DAS28(CRP). Population: ITT. Note that the SF-36 is only scored at baseline, Week 4, Week 12, and Week 24/EDV. LOCF and observed case (descriptive only at baseline and weeks 12 + 24). Tables will present the 8 domain scores and the 2 main scores.

#### **Table 14.2.1.10.1:SF-36: Descriptive statistics of the actual values**

#### **Table 14.2.1.10.2:SF-36: Descriptive statistics of the change from baseline**

#### **Table 14.2.1.10.3:SF-36: Descriptive statistics of the percent change from baseline**

(descriptive statistics at each time point; frequency table at weeks 12 + 24)

#### **Table 14.2.1.10.4:SF-36: Summary with overall p-value and pairwise comparisons versus placebo**

**Table 14.2.1.10.5: SF-36: Exploratory pairwise comparisons among the dose groups within each regimen****Table 14.2.1.10.6: SF-36: Exploratory pairwise comparisons between regimens within each daily dose level****8.10.3. Figures over the whole 24 weeks period**

Line plots showing baseline, Week 4, 12 and 24. Same analysis as for the DAS28(CRP). Population: ITT. LOCF only. Both main scores as well as the 8 subdomains will be presented.

**Figure 14.2.1.10.1: SF-36: Plot of the actual values over time****Figure 14.2.1.10.2: SF-36: Plot of the changes from baseline over time****Figure 14.2.1.10.3: SF-36: Plot of the percent changes from baseline over time****8.10.4. Tables after Week 12**

Tables will present Weeks 4, 12 and 24, unless specified otherwise, for the 15 arms of “efficacy chapter 3”. The same descriptive analysis as DAS28(CRP) will be performed. Analysis population: ITT. LOCF and observed case (weeks 12 + 24). Tables will present the 8 domain scores and the 2 main scores.

**Table 14.2.1.10.7: SF-36 after Week 12: Descriptive statistics of the actual values****Table 14.2.1.10.8: SF-36 after Week 12: Descriptive statistics of the change from baseline****Table 14.2.1.10.9: SF-36 after Week 12: Descriptive statistics of the percent change from baseline****8.10.5. Figures after Week 12**

No figures planned.

**8.10.6. Listings****Listing 16.2.6.10: SF-36: Derived summary scores**

Listing per treatment group, per subject and per time point of all derived summary scores (the 2 component scores and the 8 domain scores): actual values, changes from baseline and percent changes from baseline. The original 36 items will not be listed.

Population: ITT.

## 9. DEFINITIONS OF PHARMACOKINETICS TABLES, LISTINGS AND FIGURES

These analyses will be described in a separate SAP. A separate report will be written based on the analysis performed by [REDACTED]

## 10. DEFINITIONS OF PHARMACODYNAMICS TABLES, LISTINGS AND FIGURES

Mock tables, listings and figures are provided in a separate document.

All analyses will be run on the ITT population, unless specified otherwise.

### 10.1. PARAMETERS

Assessment: marker YKL-40 (also known as Chitinase 3 L 1, CHI3L1) in serum.

Visits to present:

- Baseline
- Week 12: this is either the Week 12 visit itself, OR the EDV visit in case the subject dropped out of the study prior to Week 12, OR the last post-baseline visit prior to Week 12.

The actual values, changes from baseline and percent changes from baseline will be derived and analyzed.

Note that the percentage change from baseline remains missing if the baseline value itself equals zero.

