### **8.7.1.3 Pharmacodynamic Assessments**

Blood samples for PD assessments will be collected in all subjects at Baseline (Day -1), Week 1, Week 4, Week 12, and Week 24 or the EDV.

Two blood samples of 2.5 mL each will be collected in 2 PAXgene tubes. Immediately after collection, the tubes will be gently inverted 8 to 10 times and stored at room temperature for a minimum of 2 hours and a maximum of 72 hours before freezing at -20°C (-4°F) for storage until further analysis (gene expression in circulating leukocytes; messenger ribonucleic acid as well as micro ribonucleic acid [miRNA] profiling).

Additionally, 1 blood sample of 8.5 ml will be collected in a SST tube. The sample will be allowed to clot in the tube for 30 minutes at room temperature, after which the tube will be centrifuged. Serum will be extracted, divided over 4 aliquots and frozen at -80°C (-112°F) until further analysis (analytes and miRNA profiling).

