#### **Table 14.2.3.3: Pharmacodynamics: YKL-40: Exploratory pairwise comparisons among the dose groups within each regimen**

**Table 14.2.3.4: Pharmacodynamics: YKL-40: Exploratory pairwise comparisons between regimens within each daily dose level**

**Table 14.2.3.5: Pharmacodynamics: YKL-40: Descriptive statistics for Week 12 ACR20 responders versus non-responders**

Same as previous table, but split up for Week 12 ACR20 responders and non-responders.

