**Table 14.2.3.6: Pharmacodynamics: YKL-40: Descriptive statistics for Week 12 ACR50 responders versus non-responders**

**Table 14.2.3.7: Pharmacodynamics: YKL-40: Descriptive statistics for Week 12 ACR70 responders versus non-responders**

**Table 14.2.3.8: Pharmacodynamics: YKL-40: Correlation with ACR20/50/70**

Relationship between the change from baseline in PD marker and ACR20 will be investigated via a logistic regression model on the ACR20 responses, with the following factors in the model: treatment groups, baseline YKL-40, change from baseline in YKL-40. ACR20 and YKL-40 will be taken from the same visit.

Same for the ACR50 and ACR70.

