**Table 14.2.3.9: Pharmacodynamics: YKL-40: Correlation with continuous efficacy parameters**

Relationship between the change from baseline in PD marker and the change from baseline in efficacy parameters will be investigated via Pearson's correlation coefficient as provided by SAS PROC CORR. Efficacy parameters and YKL-40 will all be taken from the same visit.

The following efficacy parameters will be tested:

- ACR20 components: TJC68, SJC66, the 3 VAS scores, CRP and HAQ-DI.
- Summary scores: DAS28(CRP), CDAI and SDAI.

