#### **5.4.1. Last Observation Carried Forward (LOCF)**

A missing W4 analysis visit will be imputed by the last preceding non-missing data point. This can be a baseline value.

A missing W12 analysis visit will be imputed by the last preceding non-missing data point. Again this could be a baseline value. This will only be done for the main descriptive statistics and comparisons vs placebo. Correlation analyses will be performed on OC only.

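### YKL-40 values labelled Week 12 can come from earlier visits and are paired with efficacy from those visits without a time term, which can create or inflate a marker-response association

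*SAP*

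**What the plan says.** SAP 10.1 presents YKL-40 at Baseline and Week 12. The Week 12 value is the sample from that visit, or the early discontinuation visit (EDV) for a subject who left before Week 12, "OR the last post-baseline visit prior to Week 12". Protocol 8.7.1.3 schedules PD blood at "Baseline (Day -1), Week 1, Week 4, Week 12, and Week 24 or the EDV". The only scheduled post-baseline samples before Week 12 are therefore Weeks 1 and 4, plus any EDV.

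Three outputs relate the marker to efficacy:

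- Table 14.2.3.8 is a logistic regression of ACR20, and likewise ACR50 and ACR70, on treatment, baseline YKL-40 and change in YKL-40. The pairing rule is "ACR20 and YKL-40 will be taken from the same visit".
- Table 14.2.3.9 gives Pearson correlations between changes in YKL-40 and changes in ten efficacy measures, with no covariates named. The pairing rule is "Efficacy parameters and YKL-40 will all be taken from the same visit".
- Figure 14.2.3.2 plots percent changes under the same pairing.

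Table 14.2.3.5 is a descriptive split: "Same as previous table, but split up for Week 12 ACR20 responders and non-responders". Tables 14.2.3.6 and 14.2.3.7 do the same for ACR50 and ACR70. None of the three says how a missing responder status is handled.

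The observed-case list in SAP 4.4.3 does not name YKL-40, and Section 10 plans no observed-case or completer analysis of it. The later SAP addendum covers 18 other markers. It allows carry-forward for the main descriptive statistics and comparisons with placebo, but states: "Correlation analyses will be performed on OC only".

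**The concern.** Efficacy is assessed at Weeks 1 and 4 and at the EDV (Protocol 8.7.1.1.1), so an early YKL-40 sample brings an early efficacy value with it. An early pair would tend to show little marker change and a low chance of ACR response; a Week 12 pair would tend to show more of both. A model that cannot tell the two kinds of pair apart can attribute the difference in time on drug to the marker.

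These tables exist to show whether a change in YKL-40 tracks clinical response. As specified, a reader could not tell whether a positive finding reflects that relation or the mixture of visits.

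**Working it through.** **The plan's own figures.** The documents state no figure for the YKL-40 association. Their only power figures are for ACR20 at Week 12 (Protocol 8.8.2). With 85 per arm and two-sided alpha 0.05/6 = 0.0083, a pooled chi-square calculation gives 0.898 and 0.912 against the stated 90%, and 0.809 and 0.784 against the stated 80%. They reproduce and are not affected. From them this check takes only the layout of 7 arms of 85, 595 in total.

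**Mechanism.** Let w be the share of early pairs, and dM and dE the early-versus-Week-12 shifts in mean marker and mean efficacy, in SD units. With no association within either visit, the mixture still has covariance w(1−w)·dM·dE, so

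r = w(1−w)·dM·dE / √[(1 + w(1−w)dM²)(1 + w(1−w)dE²)].

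- w = 0.10, dM = 0.3, dE = 0.8: 0.0216 / √(1.0081 × 1.0576) = 0.02.
- w = 0.20, dM = 0.7, dE = 1.0: 0.112 / √(1.0784 × 1.16) = 0.10.
- If dM = 0, then r = 0.

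The two-sided 5% critical value is about 1.96/√595 = 0.08 with all arms pooled, or about 1.96/√85 = 0.21 within one arm. SAP Table 14.2.3.9 does not say which applies.

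**Logistic model of Table 14.2.3.8, simulated under the null.** The marker is independent of response given arm and visit. All time courses and early shares are assumptions. In the first set, 30% of early values come from Week 1 and the rest from Week 4, with 1,000 runs per cell. Inputs at Weeks 1/4/12:

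- Moderate: active ACR20 12/35/58%, placebo 8/22/35%, active marker shift −0.1/−0.3/−0.5 SD.
- Strong: active 10/30/65%, placebo 6/20/40%, active marker shift −0.2/−0.5/−1.0 SD.
- Flat marker: response as in moderate, active marker shift −0.5 SD at every visit.

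The placebo marker shift is zero throughout. Rejection rate at nominal 5%, no visit term:

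| Early share | Moderate | Strong | Flat marker |
|---|---|---|---|
| 0% | 4.7% | 4.9% | 4.9% |
| 5% | 5.0% | 7.8% | 6.3% |
| 10% | 7.4% | 15.8% | 5.0% |
| 20% | 10.1% | 38.0% | 5.2% |

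At 20% early values the mean odds ratio per SD is 0.95 (moderate), 0.87 (strong) and 1.00 (flat), where the truth is 1. With a visit term (500 runs, 10% and 20% early), the moderate and strong rates return to 3.6–4.4% with odds ratios of about 1.00. In the flat scenario they are 4.8% and 7.4%, also with odds ratios of 1.00.

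**Sensitivity to when the substitutes fall.** The second set has 1,500 runs. Active ACR20 is 12/22/35/50/60% at Weeks 1/2/4/8/12, and the marker reaches 20/35/55/85/100% of its Week 12 change. Rates for 5/10/15% early values:

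| Week 12 marker change | All substitutes at Weeks 1 or 4 | Spread evenly over Weeks 1–10 |
|---|---|---|
| −0.5 SD | 5.7 / 6.7 / 8.5% | 5.3 / 5.2 / 5.5% |
| −1.0 SD | 6.6 / 12.1 / 17.7% | 5.1 / 7.0 / 9.2% |

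A separate simulation agreed: 5–8% and 6–17% for substitutes at Weeks 1 or 4, and 4–9% when spread. Observed Week 12 pairs or a time term brought the rate back to about 4–6%.

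**Upper end.** The widest contrast tried sets active ACR20 at 60% and marker change at −1.0 SD at Week 12, against 20–30% and −0.2 to −0.4 SD in early pairs. It gave 7–11%, 12–20% and 16–39% at 5, 10 and 15% early values.

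**The case against.** The strongest reply is that the effect is conditional and may be negligible. It needs YKL-40 to be still changing after the substitute visit, response to rise over the same interval, and a material share of substitutes. For dropouts, SAP 10.1 names the EDV, which can fall at any time before Week 12, and under SAP 3.3 a visit from Day 71 onward already counts as Week 12. A Week 1 substitute requires the Week 12, EDV and Week 4 samples all to be missing. This stands. A reader might infer that time on drug by itself creates an association whenever substitutes exist, or that inflation of 16–39% is to be expected. The documents support neither: they give no time course and no dropout rate, and the flat-marker case shows no bias.

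Second, the wording on pairing can be read two ways. SAP 3.3 says outputs present time points rather than visits, so the same visit could mean the Week 12 analysis time point. That removes the time-mixing mechanism but pairs a dropout's early marker with an imputed Week 12 response: non-response by rule under NRI, which SAP 4.4.3 makes primary for binary data. That is a dropout artefact instead. Tables 14.2.3.5–14.2.3.7 could share it if responder status is NRI-imputed, but the SAP does not say so, and they are descriptive with no test.

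Third, the addendum is limited precedent. It covers other markers, leaves out the 50 mg/day groups and was written after unblinding. It does not show that the main SAP is wrong; it shows only that the sponsor found the alternative workable.

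Fourth, the stakes are low. This is one exploratory marker, with three logistic models and ten correlations and no stated multiplicity control, and PD is not among the interim parameters in SAP 6.2.

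**Conclusion.** The point holds in conditional form. The label, the same-visit pairing and the absence of a time term are plain in the text, and no observed-case check on YKL-40 would reveal the problem. Whether it produces a spurious association depends on quantities the documents do not give. For 5–15% early values, the assumed trends put the false-positive rate of the Table 14.2.3.8 model between about 5% and about 17%, with higher values only under stronger contrasts or a larger early share. None of these simulations modelled informative dropout.

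Severity is minor. No primary or secondary efficacy result changes, and neither does the interim support for dose selection.

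**What to change.** Run Tables 14.2.3.5–14.2.3.9 and Figure 14.2.3.2 on observed Week 12 YKL-40 values paired with observed Week 12 efficacy, which is the addendum's rule for its correlation analyses. Alternatively, keep all pairs, add a visit or time-on-drug term to the logistic model, and use a partial correlation for Table 14.2.3.9. In either case, state whether the same visit means the actual visit or the analysis time point. Keep the substitution rule for Tables 14.2.3.1–14.2.3.4, and report per arm how many values are not from Week 12.

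The cost is SAP wording and one count per arm. Under the first option, pairs without a Week 12 sample (5–15% is assumed above) leave the exploratory analyses, which then describe only subjects with a Week 12 sample. The second option keeps everyone.
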